**APPENDIX VI: MONITORING PLAN**

A copy of the Monitoring Plan can be obtained upon request from the Clinical Project Manager for the study.

1. SYNOPSIS OF STUDY DESIGN AND PROCEDURES

1.1 Purpose of the Statistical Analysis Plan

This statistical analysis plan (SAP) is intended to provide a detailed and comprehensive description of the planned methodology and analysis to be used for Protocol 16-308 the XIENCE 90 clinical study. This plan is based on the [REDACTED] May 25, 2018 study protocol.

1.2 Study Objectives

Primary Objective: to show non-inferiority of the primary endpoint of all death or all MI (modified ARC) from 3 to 12 months following XIENCE implantation in HBR subjects treated with 3-month DAPT compared to a historical control after propensity score adjustment.

Secondary Objective:

- To show superiority of the major secondary endpoint of major bleeding (Bleeding Academic Research Consortium [BARC] type 2-5) from 3 to 12 months following XIENCE implantation in HBR subjects treated with 3-month DAPT compared to a historical control after propensity score adjustment.
- To evaluate stent thrombosis (ARC definite/probable) from 3 to 12 months following XIENCE implantation in HBR subjects treated with 3-month DAPT against a performance goal (PG).

1.3 Study Design

XIENCE 90 study is a prospective, single arm, multi-center, open label trial to evaluate the safety of 3-month dual antiplatelet therapy (DAPT) in subjects at high risk of bleeding (HBR) undergoing percutaneous coronary intervention (PCI) with the approved XIENCE family of coronary drug-eluting stents.

The XIENCE family stent systems include commercially approved^a XIENCE Xpedition Everolimus Eluting Coronary Stent System (EECSS), XIENCE Alpine EECSS or XIENCE PRO^X EECSS (OUS only)^b, XIENCE PRO^A EECSS (OUS only)^c, and XIENCE Sierra EECSS,

^a The commercially approved XIENCE stent will be used in geographies where it is commercially available

^b XIENCE PRO^X is a rebrand of the XIENCE Xpedition Stent System and is only available outside of the United States.

^c XIENCE PRO^A is a rebrand of the XIENCE Alpine Stent System and is only available outside of the United States.

which are all manufactured by Abbott Vascular, Inc, Santa Clara, USA. The above XIENCE family stent systems will hereinafter be called “XIENCE” in this study.

Approximately 2,000 subjects from approximately 100 sites globally will be registered in this study, with at least 50% of subjects in the United States (US). Study population consists of non-complex HBR subjects with up to three native coronary artery lesions (a maximum of two lesions per epicardial vessel) with reference vessel diameter between 2.25 mm and 4.25 mm. Eligibility of P2Y12 receptor inhibitor discontinuation will be assessed at 3-month follow-up. Subjects who are free from myocardial infarction (modified ARC), repeat coronary revascularization, stroke, or stent thrombosis (ARC definite/probable) within 3 months (prior to 3-month visit but at least 90 days) after stenting AND have been compliant with 3-month DAPT without interruption of either aspirin and/or P2Y12 receptor inhibitor for > 7 consecutive days are considered as “3-month clear”, and will discontinue P2Y12 receptor inhibitor and continued with aspirin monotherapy after 3-month follow-up.

All registered subjects will be followed at 3, 6 and 12 months post index procedure.

The data collected from the XIENCE 90 study will be compared with the historical control of non-complex HBR subjects treated with standard DAPT duration of up to 12 months from the XIENCE V USA study, which is a US post-approval study to evaluate the safety of XIENCE V EECSS in “all-comer” population under real-world setting.

1.3.1 Selection of Control

The XIENCE V USA historical HBR control for 3-month DAPT study is derived based on the following criteria:

Definition of non-complex HBR from XIENCE V USA

- HBR inclusion criteria (any one of the below HBR criteria):
 - Age \geq 75 years
 - History of major bleeding
 - History of stroke
 - Receiving or scheduled to receive chronic anticoagulation therapy
 - Renal insufficiency (creatinine $> 2\text{mg/dl}$)
 - Anemia (Hb $< 11\text{g/dl}$ or transfusion)
 - Thrombocytopenia (platelet count $< 100,000/\text{mm}^3$)
- Exclusion criteria for non-complex:
 - STEMI
 - LVEF $< 30\%$
 - Patients with more than 3 lesions treated during index procedure
 - Patients with more than 2 vessels treated during index procedure

- At least one lesion with RVD < 2.25 mm or > 4.25 mm (visual estimation)
- At least one lesion located in left main
- At least one lesion located in graft
- At least one in-stent restenosis lesion
- At least one lesion containing thrombus
- At least one target lesion having TIMI flow 0
- At least one target lesion with length > 32 mm by visual estimation.

The above selection criteria for the XIENCE V USA historical control aligns with the key inclusion/exclusion criteria of the XIENCE 90 Study.

For primary analysis, the XIENCE V USA non-complex HBR control subjects must be also 3-month clear, following the same logic as defined for the primary analysis population (refer to Section 1.4).

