### **5.3.1.1 General Inclusion Criteria**

1. Subject is considered at high risk for bleeding (HBR), defined as meeting one or more of the following criteria at the time of registration and in the opinion of the referring physician, the risk of major bleeding with > 3-month DAPT outweighs the benefit:
  - a)  $\geq 75$  years of age.
  - b) Clinical indication for chronic (at least 6 months) or lifelong anticoagulation therapy.
  - c) History of major bleeding which required medical attention within 12 months of the index procedure.
  - d) History of stroke (ischemic or hemorrhagic).
  - e) Renal insufficiency (creatinine  $\geq 2.0$  mg/dl) or failure (dialysis dependent).
  - f) Systemic conditions associated with an increased bleeding risk (e.g. hematological disorders, including a history of or current thrombocytopenia defined as a platelet count  $<100,000/\text{mm}^3$ , or any known coagulation disorder associated with increased bleeding risk).
  - g) Anemia with hemoglobin  $< 11\text{g/dl}$ .
2. Subject must be at least 18 years of age.
3. Subject or a legally authorized representative must provide written informed consent as approved by the Institutional Review Board (IRB)/Ethics Committee (EC) of the respective clinical site prior to any study related procedure.
4. Subject is willing to comply with all protocol requirements, including agreement to stop taking P2Y12 inhibitor at 3 months, if eligible per protocol.
5. Subject must agree not to participate in any other clinical trial for a period of one year following the index procedure.

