#### 6.1.2 *Clinical Assessments*

Subject demographics (age, gender, race), height, weight, family history of coronary artery disease (CAD), smoking status, cardiac history (myocardial infarction, diabetes mellitus, hypertension, hypercholesterolemia, and previous PCI/CABG information), subject's current cardiac status (presentation of CAD and multivessel disease) and indication of high bleeding risk (per criteria specified in Section 5.3.1.1) will be obtained and recorded in electronic case report form (eCRF).

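### The high-bleeding-risk entry criteria of the XIENCE V USA control do not match those of XIENCE 90, and the propensity variable for prior major bleeding is undefined, so it may not be the same measure in both cohorts

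*SAP*

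**What the plan says.** Protocol 5.3.1.1 admits a subject on bleeding history only with "History of major bleeding which required medical attention within 12 months of the index procedure". SAP 1.3.1, which selects the non-complex HBR control from XIENCE V USA, lists "History of major bleeding" with neither a time limit nor a medical-attention qualifier.

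Three other HBR items also differ. Control anemia can be met by transfusion as well as by hemoglobin below 11 g/dl. The XIENCE 90 renal item is creatinine of at least 2.0 mg/dl "or failure (dialysis dependent"; the control item is creatinine above 2 mg/dl and does not list dialysis. XIENCE 90 admits systemic and coagulation disorders in general, whereas the control lists only a platelet count below 100,000/mm³. SAP 1.3.1 nevertheless concludes that the control criteria align with the key XIENCE 90 criteria.

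The variable list in SAP 2.1.3 includes prior major bleeding by name only. Protocol 6.1.2, which sets out the baseline clinical data, mentions bleeding history only through the "indication of high bleeding risk (per criteria specified in Section 5.3.1.1").

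The propensity quintiles stratify the primary Death/MI non-inferiority test and the BARC 2-5 superiority test. The superiority result decides whether stent thrombosis is tested (SAP 2.1.4 and 2.2.2).

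**The concern.** There are two separate problems.

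The first is eligibility. With a historical control, the selection rule takes the place of randomization in fixing who is compared. If a control can enter through a route closed to XIENCE 90, or the reverse, the cohorts differ by design on a factor related to the tested bleeding endpoint.

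The second is measurement. A propensity score balances what is recorded. If a recorded yes means a bleed in the past 12 months in one cohort and a bleed at any recorded time in the other, the flag can look balanced while the underlying history is not. Keeping the propensity statistician blind to outcomes, and having the FDA review the score, guard against outcome-driven modeling. Neither would reveal a difference in definition unless the definition is written down.

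At stake are the bleeding superiority test, the stent thrombosis test behind it and, to the extent that bleeding history predicts death, the primary comparison.

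**Working it through.** The plan gives no figure on this point to reproduce, so the check starts from the text.

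**Step 1. Entry criteria side by side**

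| HBR item | XIENCE 90 (Protocol 5.3.1.1) | Control (SAP 1.3.1) | Can qualify in one cohort only, on this item |
|---|---|---|---|
| Prior major bleed | Medical attention needed, within 12 months | No window, no qualifier | Control: older bleed, or no medical attention |
| Anemia | Hb < 11 g/dl | Hb < 11 g/dl, or transfusion | Control: transfused with Hb of 11 or more |
| Renal | Creatinine ≥ 2.0 mg/dl, or dialysis | Creatinine > 2 mg/dl | XIENCE 90: creatinine exactly 2.0, or dialysis without a recorded value above 2 |
| Hematological or systemic | Systemic conditions, including low platelets and coagulation disorders | Platelets < 100,000/mm³ | XIENCE 90: conditions other than low platelets |
| Age ≥ 75, stroke | Listed | Listed | None |

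The anticoagulation items are also worded differently. The control has "Receiving or scheduled to receive chronic anticoagulation therapy"; XIENCE 90 has a clinical indication for at least 6 months or lifelong. I treat them as the same criterion, but the SAP should say so.

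**Step 2. The covariate**

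Protocol 6.1.2 records the HBR indication under the 12-month rule, and no other visible baseline item captures prior bleeding. If the propensity variable is built from that field, a XIENCE 90 subject whose only bleed was three years earlier is coded no. A control with the same history can be coded yes. The link from that field to the propensity variable is an inference; the SAP does not state it.

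**Step 3. Illustration of the flag mismatch alone**

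Every rate and prevalence here is assumed. The control size of 1,150 is from SAP 1.5; 1,600 assumes that 80% of the 2,000 registered subjects are 3-month clear. The two populations are identical, there is no true effect, and stratification is on the flag alone with pooled-N weights. Let q1 be the prevalence of a recent bleed and q2 of a remote one. Base 3-12 month bleeding risk is b = 8%, with risk ratios R1 (recent) and R2 (remote).

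- Flag yes: XIENCE 90 risk = b·R1; control risk = (q1·b·R1 + q2·b·R2)/(q1 + q2).
- Flag no: XIENCE 90 risk = [(1 − q1 − q2)·b + q2·b·R2]/(1 − q1); control risk = b.
- Weight of the yes stratum: w = [1,600·q1 + 1,150·(q1 + q2)]/2,750.
- Shift = w × (difference in yes) + (1 − w) × (difference in no), XIENCE 90 minus control.

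Low end (q1 = q2 = 2%, R1 = 2, R2 = 1): w = (32 + 46)/2,750 = 0.0284. The yes stratum differs by 16% − 12% = 4 points and the no stratum by 0. Shift = 0.0284 × 4 = 0.11 points.

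High end (q1 = 5%, q2 = 10%, R1 = 3, R2 = 2): w = (80 + 172.5)/2,750 = 0.0918. The yes stratum differs by 24% − 18.67% = 5.33 points and the no stratum by 8.84% − 8% = 0.84 points. Shift = 0.0918 × 5.33 + 0.9082 × 0.84 = 1.25 points.

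For scale, the standard error is √[0.08 × 0.92 × (1/1,600 + 1/1,150)] = 1.05 points, so the shift is about 0.1 to 1.2 standard errors. In this set-up it raises the apparent XIENCE 90 rate. It does not cover the entry differences in step 1.

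**The case against.** The strongest reply is that little of the harm is proven. Much of that stands, and it rules out several stronger readings a reader might infer.

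- **That the control look-back is unlimited.** SAP 1.3.1 is a short list and states no window. How XIENCE V USA recorded bleeding is not in the documents. No stated limit is as far as the text goes.
- **That this is the strongest bleeding covariate.** The list is unranked. It also holds age, hemoglobin, platelets, creatinine, chronic anticoagulation and two bleeding scores, so other bleeding-risk adjustment would remain.
- **That the covariate is known to differ.** It is undefined, and SAP 2.1.3 has redacted text. A mismatch is plausible from Protocol 6.1.2 but not stated.
- **That the anemia and renal differences distort the bleeding covariate.** They concern eligibility. Hemoglobin and creatinine are propensity variables in their own right, and the cut-off difference affects only values of exactly 2.0.
- **That controls with only a remote bleed must dilute the control bleeding rate.** That depends on how they compare with the other controls, not with recent bleeders. In the illustration, remote bleeders run at 8% to 16%, at or above the base rate.
- **That Protocol 2.1 shows recency matters for Death/MI.** It reports deaths within 1 year of a bleed in trials of DAPT duration. A qualifying bleed 0 to 12 months before index places the 3-12 month endpoint window 3 to 24 months after the bleed, partly outside that year, and pre-procedure bleeding history is a different setting.

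It is also fair that a flag mismatch in the illustrated direction would be conservative for both tests. That does not settle the matter, because the direction of the transfusion and other entry differences is unknown. The objection leaves untouched the plain contradiction between the two lists and the statement that they align.

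**Conclusion.** The point holds as a defect of definition. As written, SAP 1.3.1 can admit controls who would not qualify for XIENCE 90, and XIENCE 90 can admit subjects the control list would not select, under a statement that the criteria align. The prior-bleeding propensity variable may not measure the same thing in both cohorts, and checking balance on the recorded flag would not reveal it. The visible sensitivity analyses (quartiles in SAP 2.2.1; medication compliance and missing outcomes in SAP 2.9, part of which is redacted) do not address this.

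The documents do not support a claim that either comparison is biased by a known amount or in a known direction. The 0.1 to 1.25 points above illustrate one mechanism and rest on assumed prevalences and risks, identical populations and a single-flag stratification. They show only that the effect could range from negligible to about the size of the standard error.

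**What to change.** 1. If XIENCE V USA holds bleed dates, apply the 12-month limit to control selection and to the propensity variable. If it does not, state in the SAP that the variable differs between the cohorts, and give the definition and look-back for each.
2. Use one creatinine cut-off in both cohorts, and the dialysis criterion wherever it is recorded.
3. Add a sensitivity analysis that repeats the primary non-inferiority test and the bleeding superiority test with both cohorts restricted to subjects who meet at least one HBR criterion defined the same way in both. This removes subjects who qualify only through bleeding history, transfusion, or a systemic or coagulation disorder other than low platelets. Leave the bleeding-history variable out of the propensity model for this run. The documents do not list the components of the two bleeding scores; if either uses prior bleeding, treat that input in the same way.
4. Replace the alignment sentence in SAP 1.3.1 with a list of the differences that remain.

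The cost is SAP wording, one extra run and slightly smaller cohorts in that run. The main control shrinks slightly if dates allow the 12-month limit. Collecting dated remote bleeds for 2,000 XIENCE 90 subjects across about 100 sites may not be cheap, and this fix does not need it.

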Key Inclusion Criteria	
General Inclusion Criteria
 
 
1. Subject is considered at high risk for bleeding (HBR), defined as meeting one or more of the following criteria at the time of registration and in the opinion of the referring physician, the risk of major bleeding with > 3-month DAPT outweighs the benefit: 
 
a) <math>\geq 75</math> years of age.
 
b) Clinical indication for chronic (at least 6 months) or lifelong anticoagulation therapy.
 
c) History of major bleeding which required medical attention within 12 months of the index procedure.
 
d) History of stroke (ischemic or hemorrhagic).
 
e) Renal insufficiency (creatinine <math>\geq 2.0</math> mg/dl) or failure (dialysis dependent).
 
f) Systemic conditions associated with an increased bleeding risk (e.g. hematological disorders, including a history of or current thrombocytopenia defined as a platelet count <math><100,000/\text{mm}^3</math>, or any known coagulation disorder associated with increased bleeding risk).
 
g) Anemia with hemoglobin <math>< 11\text{g/dl}</math>.
 
 
 
2. Subject must be at least 18 years of age.
 
3. Subject or a legally authorized representative must provide written informed consent as approved by the Institutional Review Board (IRB)/Ethics Committee (EC) of the respective clinical site prior to any study related procedure.
 
4. Subject is willing to comply with all protocol requirements, including agreement to stop taking P2Y12 inhibitor at 3 months, if eligible per protocol.
 
5. Subject must agree not to participate in any other clinical trial for a period of one year following the index procedure.
 
 
Angiographic Inclusion Criteria
 
 
1. Up to three target lesions with a maximum of two target lesions per epicardial vessel. Note: 
 
• The definition of epicardial vessels means left anterior descending coronary artery (LAD), left circumflex coronary artery (LCX) and right coronary artery (RCA) and their branches. For example, the patient must not have >2 lesions
 
 
 

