#### **Angiographic Exclusion Criteria**

1. Target lesion is in a left main location.
2. Target lesion is located within an arterial or saphenous vein graft.
3. Target lesion is restenotic from a previous stent implantation.
4. Target lesion is a total occluded lesion (TIMI flow 0).

	

5. Target lesion contains thrombus as indicated in the angiographic images (per SYNTAX score thrombus definition).

6. Target lesion is implanted with overlapping stents, whether planned or for bailout.

 
Note: If there is more than one target lesion, all target lesions must satisfy the angiographic eligibility criteria. Non-target lesion (i.e., lesions that do not meet the angiographic criteria listed above) treatments are not allowed during the index procedure.

Primary Analysis Population	The primary analysis population is “3-month clear” population, defined as subjects who are free from myocardial infarction (modified ARC), repeat coronary revascularization, stroke, or stent thrombosis (ARC definite/probable) within 3 months (prior to 3-month visit but at least 90 days) after stenting AND have been compliant with 3-month DAPT without interruption of either aspirin and/or P2Y12 receptor inhibitor for > 7 consecutive days.

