#### **5.3.2.1 Angiographic Inclusion Criteria**

1. Up to three target lesions with a maximum of two target lesions per epicardial vessel.

Note:

- The definition of epicardial vessels means left anterior descending coronary artery (LAD), left circumflex coronary artery (LCX) and right coronary artery (RCA) and their branches. For example, the patient must not have >2 lesions requiring treatment within both the LAD and a diagonal branch in total.

- If there are two target lesions within the same epicardial vessel, the two target lesions must be at least 15 mm apart per visual estimation; otherwise this is considered as a single target lesion.

2. Target lesion  $\leq$  32 mm in length by visual estimation.
3. Target lesion must be located in a native coronary artery with visually estimated reference vessel diameter between 2.25 mm and 4.25 mm.
4. Exclusive use of XIENCE family of stent systems during the index procedure.
5. Target lesion has been treated successfully, which is defined as achievement of a final in-stent residual diameter stenosis of  $<20\%$  with final TIMI-3 flow assessed by online quantitative angiography or visual estimation, with no residual dissection NHLBI grade  $\geq$  type B, and no transient or sustained angiographic complications (e.g., distal embolization, side branch closure), no chest pain lasting  $> 5$  minutes, and no ST segment elevation  $> 0.5$  mm or depression lasting  $> 5$  minutes.

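### SAP 1.3.1 selects controls by number of vessels treated, not lesions per vessel, and omits the overlapping-stent exclusion, so its alignment statement is wrong on these two points

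*SAP*

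**What the plan says.** **Control.** Under the title "Definition of non-complex HBR from XIENCE V USA", SAP 1.3.1 lists the HBR criteria and then eleven exclusions that make a control non-complex. One removes anyone with more than three lesions treated; the next removes "Patients with more than 2 vessels treated during index procedure". Nothing in the list limits lesions within one vessel, and nothing mentions overlapping stents. The list shows no redaction. It closes with the statement: "The above selection criteria for the XIENCE V USA historical control aligns with the key inclusion/exclusion criteria of the XIENCE 90 Study".

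**Trial.** The Protocol Summary (Key Inclusion Criteria) and Protocol 5.3.2.1 admit "Up to three target lesions with a maximum of two target lesions per epicardial vessel". No limit is placed on the number of vessels. A note in 5.3.2.1 makes the count apply to a vessel together with its branches: "the patient must not have >2 lesions requiring treatment within both the LAD and a diagonal branch in total". The Protocol Summary (Key Exclusion Criteria) and 5.3.2.2 exclude a subject when "Target lesion is implanted with overlapping stents, whether planned or for bailout", and Protocol 6.2 repeats that such subjects are not to be registered. SAP 1.3 itself gives the lesions-per-vessel limit when it describes the XIENCE 90 population.

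**Source of the controls.** SAP 1.3 describes XIENCE V USA only as a study "which is a US post-approval study to evaluate the safety of XIENCE V EECSS in “all-comer” population under real-world setting". Its own eligibility rules and data coding are not shown.

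**The concern.** The trial has a single arm. Both the primary non-inferiority test and the bleeding superiority test take their comparator from SAP 1.3.1. A cap on vessels and a cap on lesions per vessel are different rules and admit different patients. Followed as written, 1.3.1 can keep controls that XIENCE 90 would have refused (three lesions in one vessel, overlapping stents) and drop controls that it would have accepted (one lesion in each of three vessels). A reader who trusts the alignment sentence would believe that the two groups met the same lesion rules.

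The difference in rates is XIENCE 90 minus control. Anything that raises the control rate makes non-inferiority easier to show, and anything that lowers it makes it harder. The mismatch could act either way.

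**Working it through.** **1. The rules side by side**

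| Rule | XIENCE 90 | Control (SAP 1.3.1) |
|---|---|---|
| Lesions treated | at most 3 | at most 3 |
| Lesions per epicardial vessel | at most 2 | no limit |
| Vessels treated | no limit | at most 2 |
| Overlapping stents | excluded | not mentioned |

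The other ten of the eleven exclusions have a direct XIENCE 90 counterpart: STEMI, LVEF, more than three lesions, reference vessel diameter, left main, graft, restenosis, thrombus, TIMI flow 0 and lesion length.

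**2. Where the vessel rules disagree**

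Protocol 5.3.2.1 and Appendix II recognise three epicardial vessels: LAD, LCX and RCA. I assume that XIENCE V USA counts vessels and lesions in the same way. The ways to place lesions in three vessels are then:

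- 1 lesion: 3
- 2 lesions: 6
- 3 lesions: 10
- total: 3 + 6 + 10 = 19

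The XIENCE 90 rule rejects the three placements with all three lesions in one vessel and accepts 19 − 3 = 16. The control rule rejects the single placement with one lesion in each vessel and accepts 19 − 1 = 18. Both accept 15. The 4 discordant placements are:

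- one lesion in each of three vessels (1 placement): XIENCE 90 only
- three lesions in one vessel (3 placements): control only

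Overlapping stents add a one-way difference, excluded in XIENCE 90 and not in the control.

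**3. What the propensity score can do**

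SAP 2.1.3-1 lists numbers of lesions, vessels and stents, and total lesion and stent length. It lists neither overlap nor lesions per vessel. On the same coding assumption, no control has three vessels treated, so three-vessel XIENCE 90 subjects are compared with controls who had fewer vessels treated. Stratification cannot supply controls that were never selected.

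**4. Size of any effect (illustration only)**

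Suppose a share f of the controls would be ineligible under the XIENCE 90 rules and has risk ratio RR against the remaining controls, whose event rate is p. The control rate becomes p(1 − f) + p·f·RR, a shift of p·f·(RR − 1). The documents give none of these inputs. With p from 4% to 8% and RR from 0.5 to 2, all assumed, the extremes occur at p = 8%:

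- f = 1%: 0.08 × 0.01 × (−0.5) = −0.04 points, to 0.08 × 0.01 × 1 = +0.08 points
- f = 5%: −0.20 to +0.40 points
- f = 10%: −0.40 to +0.80 points

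At RR = 1 the shift is zero. Nothing in the documents favours any row.

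**5. Precision after re-selection**

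SE = √[p(1 − p)(1/n_t + 1/n_c)], unstratified. I assume p = 5.5% and n_t = 1,700 (85% of the 2,000 in SAP 1.5). SAP 1.5 gives n_c of about 1,150.

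- n_c = 1,200: SE 0.860 points
- n_c = 1,150: SE 0.870 points
- n_c = 1,000: SE 0.909 points

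The ratio for 1,000 against 1,150 is √[(1/1,700 + 1/1,000)/(1/1,700 + 1/1,150)] = 1.044, whatever the event rate.

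**The case against.** **The word key.** The Protocol Summary prints essentially the full eligibility list under its Key headings, including consent and pregnancy. No retrospective selection could mirror all of that, so the SAP's use of the word need not cover every item. This is fair, and it shields the list as a whole, since ten of eleven exclusions correspond. It does not explain why one listed rule limits a different quantity, when SAP 1.3 had just given the trial's limit as two lesions per vessel.

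**Coding.** SAP 1.3.1 says vessels, not epicardial vessels. XIENCE 90 also merges same-vessel lesions less than 15 mm apart and treats the last staged procedure as the index procedure. Whether XIENCE V USA counted in these ways is unknown. This stands: the 4-of-19 count depends on it. The difference in wording and the missing overlap rule do not.

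**Mitigation.** The listed covariates are partial proxies for lesions per vessel and overlap, the 32 mm limit on lesion length applies to controls, and the propensity results go to FDA before any outcome analysis. Redacted text in SAP 2.1.3 and 2.9 may hold related rules. All of this lowers the likely impact. None of the visible text reconciles the two rules.

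**Re-selection has its own risk.** Control outcomes already exist. This is a reason to have the selection made blind to them, not to leave the rule as it is.

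**Stronger readings that the documents do not support.** A reader might infer that the SAP defines non-complex HBR twice. It does not: SAP 1.3 describes the trial population, and only 1.3.1 gives a definition, for the control. A reader might take 4 of 19 as a share of patients, but patient frequencies are not given. A reader might conclude that the non-inferiority test is biased or its type I error inflated, but no affected number or risk difference is available. Other wording differences, such as the 12-month limit on bleeding history or transfusion counting as anemia, may not be real population differences, because XIENCE V USA's own rules are not shown.

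**Conclusion.** The point holds as a mismatch of rules on two items: vessels treated in place of lesions per vessel, and no overlapping-stent exclusion. On these the alignment sentence is incorrect; on the other non-complex exclusions it is sound. Confidence is high for the wording. That the vessel rules disagree in both directions rests on the assumption that XIENCE V USA codes lesions and vessels as XIENCE 90 does. The number of affected controls and the size and direction of any bias cannot be determined from the documents, and the propensity covariates adjust in part. It should still be corrected, because the list selects the comparator for the primary test and the change is cheap.

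**What to change.** In SAP 1.3.1:

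1. Replace the vessel-count exclusion with: more than 2 lesions treated in any one epicardial vessel. Exclude controls with overlapping stents where XIENCE V USA recorded this. Both rules need only index-procedure data, so the outcome-blinded independent statistician of SAP 2.1.3 can apply them before the propensity design is finalised.
2. Correct the alignment sentence. State which of these rules, if any, cannot be applied. Report the numbers of controls added and removed and the revised control N.
3. Only if re-selection is not possible, keep the current control and add one propensity-stratified sensitivity analysis of the primary endpoint. Restrict it to subjects in both groups who meet both rule sets: at most 2 lesions per vessel, at most 2 vessels treated, no overlapping stents. After re-selection this analysis would only remove three-vessel subjects, so it is not needed as well.

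**Cost.** A wording change and one blinded re-run of control selection on existing data. Control N may rise as three-vessel controls return, or fall as others leave. Precision should change little: even a fall from 1,150 to 1,000 controls would widen the standard error by 4.4%, assuming 1,700 XIENCE 90 subjects. If overlap was not recorded in XIENCE V USA, it remains a stated limitation.
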